## 1.0 Introduction and Background

Every year, approximately 70,000 young adults (ages 18-39) are diagnosed with cancer, which can significantly affect their health-related quality of life in multiple areas, including the potential for infertility or other reproductive challenges. Despite this, very few young adults diagnosed with cancer are actually provided fertility preservation information let alone effective strategies or tools for how to best navigate their fertility preservation options. **It is critical to provide decision-making information and support about infertility risk and existing interventions to maintain reproductive potential in a delivery mode that is most congruent with this population's health communication style, such as mHealth applications.** Numerous organizations, including the American Society for Reproductive Medicine (ASRM), American Society of Clinical Oncology (ASCO), and the National Comprehensive Cancer Network (NCCN), have established national guidelines to enhance provider adherence and facilitate patient and provider discussions about fertility preservation options prior to proceeding with fertility compromising treatments. These guidelines recommend that 1) all oncologists inform their patients about the impact of their cancer and/or treatment on their fertility, and 2) all patients who solicit information about fertility preservation receive it, including a referral to a reproductive specialist when appropriate. However, previous studies suggest that oncologists face many communication challenges when discussing fertility preservation with their patients. These challenges can be related to physician attributes (e.g., knowledge barriers), patient attributes (e.g., cultural or religious prohibitions for assisted reproduction), and healthcare factors (e.g., time demands). In fact, a burgeoning scientific literature exists on adult oncology providers' practice patterns and barriers to discussing fertility preservation and suggests that **oncologists rarely refer patients to fertility preservation specialists with less than 25% being aware of or distributing written educational materials to their patients and <50% following recommended ASRM/ASCO/NCCN guidelines.** Similar trends hold true for the dearth of fertility preservation information and support provided to young adult cancer patients. When more than one specialist is involved (commonly the case in young adult care), information on fertility preservation may be neglected as one specialist may assume another already discussed the topic with the patient.

**Given these provider-centered obstacles, it is essential that patients can receive timely and accurate fertility preservation information via non-provider channels so they can be empowered to ask specific questions and be engaged to make appropriate decisions on their own behalf.** mHealth interventions represent promising options for patient engagement, especially within a younger demographic such as young adults with cancer. Technology-enabled communications are increasingly utilized, accessible, and can be tailored to reflect specific values and preferences of a population. **By delivering guideline-based fertility preservation information to young adult patients using mHealth technologies, patient knowledge may be increased and sustained, and both patients and providers may be more empowered to attend to this unaddressed issue through shared decision-making.**

This study will utilize advances in mHealth technologies to address knowledge deficits,

enhance self-efficacy, and promote shared decision-making about fertility options among newly diagnosed young adults with cancer and their providers. We will achieve this goal by developing an mHealth tool (Fertilite) to increase patient knowledge, thereby positively impacting self-efficacy for fertility preservation decision-making, and enhancing satisfaction with fertility preservation decisions made for this group of underserved patients. The use of mHealth interventions has grown significantly in recent years, increasing the potential to make decision-making interventions more accessible, personally tailored, and integrated into clinical practice.

## **2.0 Objectives**

### **2.1 Primary Objective**

**2.1.1 Adapt and optimize fertility preservation content in a tailored mHealth tool for fertility preservation decision-making.** More specifically, we will adapt fertility-preservation content for tailored, rapid, and clear dissemination of information in an engaging, cross-platform, patient-friendly mHealth format. We will alpha-test this tool with an ethnically diverse sample of cross-cultural end users to collect qualitative data and evaluate usability to refine content and design. No formal hypothesis testing will be done.

### **2.2 Secondary Objective**

**2.2.1** To qualitatively evaluate comprehensibility of the mHealth tool.

### **2.3 Exploratory Objectives**

- 2.3.1 To describe the characteristics of the study population in terms of health literacy, sociodemographics, technology use, and eHealth literacy.
- 2.3.2 To explore differences in usability by health literacy, sociodemographic characteristics, technology use, and eHealth literacy.

## **3.0 Study Population**

Young adult patients are eligible if they: 1) are ages 18 to 39; 2) had a histologically confirmed diagnosis of cancer during ages 15 to 39, 3) will be receiving or have received treatment associated with a risk of infertility (i.e., systemic chemotherapy, pelvic radiotherapy, and/or pelvic surgery with potential impact on reproductive function), 4) considered or wish they had considered fertility preservation treatments, 5) are able to speak, read, and understand English, and 6) are able to provide electronic informed consent 7) have access to the internet 8) have access to a computer that will allow for a WebEx research interview. Young adult patients will be excluded if they: 1) had an infertility diagnosis prior to cancer diagnosis, 2) had a history of fertility preservation or fertility treatments prior to their cancer diagnosis, 3) are more than five years post-cancer-related treatments (i.e., systemic chemotherapy, pelvic radiotherapy, and/or pelvic

Fertilite  
Wake Forest Baptist Comprehensive Cancer Center (WFBCCC)  
WFBCCC # 01717

surgery). The electronic medical record will be queried to identify potentially eligible patients. IRB-approved study flyers may also be disseminated through email blasts or postings on websites of local cancer support agencies such as Cancer Services. Once potential participants have been identified, a study team member will contact patients by phone, email, and/or MyWakeHealth to describe the study, answer questions, confirm eligibility, and consent those who are interested.

Alpha testing will occur with 24 young adults. For this purposive sample, we will recruit equal numbers of men and women, one half (n=12) of our sample will be from racial or ethnic minority groups, and one fourth (n=6) will have low literacy (i.e., <12 years of education). We will recruit participants in three phases that correspond to three rounds of computer prototype testing (Round 1, n=6; Round 2, n=6; Round 3, n=12). We will strive for target representation of racial or ethnic minorities and low literacy participants within each phase.

## 4.0 Methods

### 4.1 Registration Procedures

All patients entered on any WFBCCC trial, whether treatment, companion, or cancer control trial, **must** be linked with a study protocol in EPIC or WISER if non Wake patient within 24 hours of Informed Consent. Patients **must** be registered prior to the initiation of the study.

We will perform the following steps in order to ensure prompt registration of our patients:

- 1.0 Complete the Eligibility Checklist (Appendix A)
- 2.0 Complete the Protocol Registration Form (Appendix B)
- 3.0 Alert the Cancer Center registrar by phone, *and then* send the electronic signed Informed Consent Form, Eligibility Checklist and Protocol Registration Form to the registrar, either by fax or e-mail.

Contact Information:

Protocol Registrar [contact]

Protocol Registrar [contact]

Protocol Registrar E-MAIL ([[contact]](mailto:[contact]))

\*Protocol Registration is open from 8:30 AM - 4:00 PM, Monday-Friday.

- 4.0 Fax/e-mail ALL eligibility source documents with registration. Patients **will not** be registered without all required supporting documents.

Note: If labs were performed at an outside institution, provide a printout of the results. Ensure that the most recent lab values are sent.

To complete the registration process, the Registrar will:

- assign a patient study number
- register the patient on the study

## 4.2 Study Procedures

Led by [name] (Co-I) and supported by [name] (Senior Analyst and Programmer), we will configure and enable technological specifications of the alpha version of our cross platform, web-based decision-making tool. Fertilite will leverage the technical infrastructure from [name] validated mPath platform (1R01CA178941), and since Fertilite will be web-based and cross-platform, it will be accessible across multiple different user systems and not limited to a tablet or smartphone (e.g., Android, iPhone). Further, Informed by the Ottawa Decision Support Framework, self-efficacy theory, and existing fertility preservation decision-aids, we expect Fertilite to include, but not be limited to, the following modules: (1) personal information, values, and preferences; (2) fertility risks and options; (3) personal stories; (4) financial concerns; (5) frequently asked questions; (6) additional resources; and (7) session summary. Across all modules, the goal will be to provide tailored information (by gender) about the risks of infertility and options to preserve fertility if interested.

**Alpha Testing with Patients.** Aim 1 qualitative activities will be supported by the Developing Shared Resource, Q-PRO (Qualitative and Patient-Reported Outcomes) of the Wake Forest Baptist Comprehensive Cancer Center (WFBCCC). Once Fertilite alpha content has been developed, we will begin pilot testing the material with consented patients (n=6). Patients will meet virtually through WebEx or individually in a private setting with a member of the research team.. Participants will review a computer prototype of Fertilite alpha content and its design elements (see <https://fertilite.phs.wakehealth.edu/>). Using an interview guide (Appendix C), a research team member will ask about issues of content, functionality, and ease of use (i.e., comprehensibility and usability). Interviews will be completed within 45-60 minutes. Alpha testing will be audio and video recorded and transcripts will be de-identified prior to subsequent qualitative coding by research team member and [name]. All participants will complete an interviewer administered screener for health literacy and self-report items for technology use, eHealth literacy, and need for cognition. Input will be used to modify Fertilite for a second round of computer prototype testing (n=6 new patients) which will follow the same process as before.

After two rounds of computer prototype testing have been completed, our

team will then review participant input and incorporate pertinent changes into a revised version of our decision aid that will be pilot tested with an additional 12 new patients who will use Fertilit-e on an iPad. As with earlier rounds of computer prototype testing, all participants will meet individually with a research team member in a private location. We will use the “Think Aloud” protocol to examine how individuals interact with and interpret Fertilit-e. A research team member will also ask each participant additional questions about the clarity of content and ease of use following an interview guide. At the end of alpha testing, participants will receive \$25. Feedback will be examined systematically by the study team and Advisory Board after each round of computer prototype testing to make necessary modifications prior to pilot testing in a subsequent aim.

## **5.0 Outcome Measures**

### **5.1 Primary and Secondary Outcomes**

To evaluate Fertilit-e alpha, we will examine its comprehensibility and design through a series of think aloud interviews and usability with additional open-ended questions (See Appendix C). We will complement the qualitative data by administering the System Usability Scale. After our alpha testing, we will have an eHealth decision aid on fertility preservation (Fertilit-e) ready to be field tested in a sample of newly diagnosed young adults with cancer.

## **6.0 Analytic Plan**

### **6.1 Analysis of Primary Outcome**

Q-PRO staff will review qualitative data to provide an integrative summary and identification of key points, potential themes, and areas of further exploration. A summary report will be created using the interview recordings and interviewer field notes. The report would include a summary for each module based on the data from the Think Aloud and Interview Guide that incorporates usability for Fertilit-e alpha. Q-PRO will also include a section on general comments and overall recommendations. Finally, they will be maintaining a spreadsheet that includes data for the sequence of modules selected, modules skipped, and overall time spent using the app. Q-PRO will then move to standard analysis (transcription, thematic analysis, saturation, etc.) for beta testing.

Our study team will calculate descriptive statistics for the System Usability Scale by gender and race/ethnicity.

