### **6.2 Analysis of Secondary Outcome**

Q-PRO staff will review qualitative data that incorporates and summarizes comprehensibility for Fertilit-e alpha using the same techniques and approaches as described above (Section 6.1).

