### 6.3 Analysis of Exploratory Outcomes

We will calculate descriptive statistics (means and standard deviations, frequencies) for all sociodemographic variables, the health literacy scale, the technology use items, the eHealth literacy scale, and the Need for Cognition – short form^34 to describe the study population. This will be considered exploratory due to the small sample size and intentional selection of participant groups.

To explore differences in usability by health literacy, sociodemographic characteristics, technology use and eHealth literacy, we will use t-tests, ANOVAs, and correlations to examine the relationship between these variables and the outcome of the System Usability Scale score.

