### 6.4 Sample Size and Power

The combined sample size from each round of computer prototype testing (N=24) should permit us to achieve data saturation for gender (12 men and 12 women). With 24 participants, we will also be able to estimate the usability data within  $\pm 0.4$  SD for the System Usability Scale using 2-sided 95% confidence intervals (CIs).

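### Does the case for N=24 in section 6.4 rest on results that sections 6.1 to 6.3 never list?

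*Combined protocol and SAP*

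**What the plan says.** Section 6.4 gives two reasons for 24 participants. The first is qualitative: the number "should permit us to achieve data saturation for gender (12 men and 12 women"). The second is precision: with 24 participants the usability data can be estimated within ±0.4 "SD for the System Usability Scale using 2-sided 95% confidence intervals (CIs").

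The other parts of section 6 describe the analyses:

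- **6.1, SUS.** "Our study team will calculate descriptive statistics for the System Usability Scale by gender and race/ethnicity".
- **6.1, interviews.** For alpha testing there is a summary report by module, with key points and potential themes, general comments and recommendations, and a spreadsheet on navigation and time. After that, "Q-PRO will then move to standard analysis (transcription, thematic analysis, saturation, etc.) for beta testing".
- **6.2.** Comprehensibility is summarised "using the same techniques and approaches as described above (Section 6.1").
- **6.3.** The population measures are described: "We will calculate descriptive statistics (means and standard deviations, frequencies) for all sociodemographic variables", followed by the literacy, technology and cognition measures. For the SUS, "we will use t-tests, ANOVAs, and correlations to examine the relationship between these variables and the outcome of the System Usability Scale score".

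Section 3.0 sets the recruitment targets: "we will recruit equal numbers of men and women, one half (n=12) of our sample will be from racial or ethnic minority groups".

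**The concern.** A sample-size rationale normally points to a result that the analysis section then lists. Here neither reason seems to. Saturation supports N=24 in 6.4, but 6.1 names it only for a later stage of testing. The ±0.4 SD applies to all 24 participants, but the SUS descriptives in 6.1 are by gender and race/ethnicity, and in 6.3 the SUS appears only as the outcome of comparisons and correlations.

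Two things could follow. If 6.1 to 6.3 were read as a complete list of outputs, the one SUS estimate whose precision is stated would go unreported. And a reader might apply ±0.4 SD to the means of groups of 12, where it is too narrow, and so think the group results firmer than they are.

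**Working it through.** **Inputs.** N=24, the two-sided 95% level and 12 men and 12 women come from 6.4. Equal numbers by sex and 12 participants from minority groups come from 3.0. The documents give no SUS standard deviation, so every figure is in SD units. All 24 are assumed to have a SUS score; no allowance for missing scores is stated.

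**The plan's own figure.** The half-width for one mean is q/√n, where q is the 97.5% quantile.

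- Normal: 1.960/√24 = 1.960/4.899 = 0.400.
- Student t, 23 df: 2.069/4.899 = 0.422.

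Both round to 0.4, so the stated precision is correct for the group it names.

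**A group of 12.**

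- Normal: 1.960/√12 = 1.960/3.464 = 0.566.
- Student t, 11 df: 2.201/3.464 = 0.635.

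| Quantile | n=24 | n=12 | Ratio |
|---|---|---|---|
| Normal | 0.400 | 0.566 | 1.41 |
| t | 0.422 | 0.635 | 1.50 |

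The fair comparison stays within one row. Setting the t figure for 12 against the stated 0.4 gives 0.635/0.400 = 1.59, but part of that is only the change of quantile.

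**Which groups have 12?** By target, men and women do, although the questionnaire's gender item has a third option, so even this split is a target. Race/ethnicity groups have 12 each only if the split is minority against all others. Section 6.1 does not say so, and finer categories would be smaller with wider intervals.

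**Difference between two groups of 12, equal SDs assumed.** t on 22 df × √(2/12) = 2.074 × 0.408 = 0.847 SD. This is also the observed difference, in units of the pooled SD, that a two-sample t-test needs to reach two-sided 5%. Section 6.3 plans t-tests and ANOVAs of the SUS by sociodemographic characteristics, and the questionnaire's sociodemographic items include gender, ethnicity and race. The planned analysis therefore already applies the wider yardstick of about 0.85 SD to group differences, not ±0.4 SD.

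**Is the overall interval outside the plan?** No. Section 6.4 belongs to section 6.0, the Analytic Plan, and says what will be estimated, from how many people and with which interval. Descriptives by subgroup in 6.1 do not exclude a total, and nothing calls 6.1 to 6.3 exhaustive. The parenthesis in 6.3 that names means, SDs and frequencies covers the population measures listed there; it does not define the SUS descriptives in 6.1.

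**Is saturation contradicted?** No. The wording in 6.4 is about what 24 interviews should allow. Section 4.2 provides for qualitative coding of the alpha transcripts and 6.1 for identifying potential themes. A formal saturation assessment is named only for beta testing, which is compatible with expecting the alpha sample to be large enough.

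**The case for a change.** The best case for a change is that it is cheap and the literal gap is real. One sentence in 6.1 could list the overall SUS mean with its interval, and one in 6.4 could give the precision for a group of 12. With so small a sample and no formal hypothesis testing under the primary objective (2.1.1), estimates with intervals are the natural output, and the only precision figure in the plan does not describe the groups that 6.1 reports. Saturation would also read better if 6.1 and 6.4 used it alike.

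The cross-reference between 6.1 and 6.4 is indeed loose, and group results will be clearly less precise than the overall one. The harm does not stand. It needs a reader to move a figure labelled for 24 participants onto groups of 12, and to ignore the group tests in 6.3 and that section's caution about small numbers and intentional selection.

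The gain is also limited. The 24 come from three rounds (6, 6 and 12), the tool is revised between rounds, and the last round uses an iPad. A pooled SUS mean therefore averages over successive versions, and a line listing its interval would add little to what the team learns from the round-by-round review.

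**Conclusion.** No change follows. The ±0.4 SD is right for the 24 participants it is stated for (0.400 normal, 0.422 t). A gender group of 12 has 0.566 or 0.635 SD, a widening by 1.41 or 1.50, and the plan claims nothing narrower for such groups. What is missing is an explicit line for an overall SUS mean and interval, which an analyst would produce from 6.4 in any case, and a consistent use of the word saturation, which in 6.4 is only an expectation. Nothing here shows that 24 is too few, and the data collected, the round-by-round revisions and the summary report do not depend on the point.

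This rests on three assumptions: all 24 participants give a SUS score; the gender target of 12 and 12 is met; and 6.4 is read as part of the Analytic Plan in which it stands. The group figures carry over to race/ethnicity only for a two-way split.

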### **6.2 Analysis of Secondary Outcome**

Q-PRO staff will review qualitative data that incorporates and summarizes comprehensibility for Fertilit-e alpha using the same techniques and approaches as described above (Section 6.1).

### 6.3 Analysis of Exploratory Outcomes

We will calculate descriptive statistics (means and standard deviations, frequencies) for all sociodemographic variables, the health literacy scale, the technology use items, the eHealth literacy scale, and the Need for Cognition – short form^34 to describe the study population. This will be considered exploratory due to the small sample size and intentional selection of participant groups.

To explore differences in usability by health literacy, sociodemographic characteristics, technology use and eHealth literacy, we will use t-tests, ANOVAs, and correlations to examine the relationship between these variables and the outcome of the System Usability Scale score.

### 6.4 Sample Size and Power

The combined sample size from each round of computer prototype testing (N=24) should permit us to achieve data saturation for gender (12 men and 12 women). With 24 participants, we will also be able to estimate the usability data within  $\pm 0.4$  SD for the System Usability Scale using 2-sided 95% confidence intervals (CIs).

### 6.5 Accrual Rate

The WFBCCC sees a high volume of young adults with cancer annually. In the last fiscal year, 901 young adults with cancer were seen and ~550 of those were post-treatment survivors. For this purposive sampling strategy, we anticipate recruiting 24 young adults within 4 months (or 6 young adults/month). Given the relatively large sample sizes of young adults at WFBCCC, we believe our proposed sample sizes and timeline are realistic goals.

